Test Product, Dose, and Administration	
AK002 Drug Product: 10 mL supplied in 10R Type 1 clear glass vials for IV infusion with [REDACTED] pH 6.0, in water for injection (WFI).
 
There is no placebo in this study.
 
AK002 at a dose of 1 mg/kg will be prepared according to the patient's body weight and administered via infusion pump on Extension Day 1. Starting with the second infusion (Extension Day 29), the dose of AK002 will be increased to 3 mg/kg AK002, and 3 mg/kg will be administered for infusions 2 through 26. Patients will be observed for 1 hour after the end of dosing.
 
Dosing will occur every 28 (\pm3) days for a total of 26 monthly doses. Dosing will occur on: Days 1, 29, 57, 85, 113, 141, 169, 197, 225, 253, 281, 309, 337, 365, 393, 421, 449, 477, 505, 533, 561, 589, 617, 645, 673, and 701 (\pm3 days). If a monthly infusion is delayed so that it occurs closer in the time frame to the next upcoming infusion, the late infusion will be considered skipped and may be made up after Day 701. Therefore, dosing could possibly occur on Day 729 (makeup for 1 skipped dose) and every 28 (\pm3) days after that, until 26 doses in total have been received.
 
Prior to the first infusion of AK002, 60 mg oral prednisone will be given 12-24 hours prior to the infusion. The initial IV infusion should be given over at least a 4-hour period, and the second infusion should be given over at least a 3-hour period. Subsequent IV infusions (3-26) can be given over approximately 1 to 4 hours, depending on the patient's tolerance of the previous infusions and at the Investigator's discretion. Infusion rate schedules are described in more detail in the Pharmacy Manual.

Duration of Patient Participation	
If no doses are considered skipped or missed, the total study duration for each patient will be approximately 28 months, which includes:
 
 • A treatment period of monthly AK002 infusions, administered every 28 (± 3) days in an open-label manner for a maximum of 26 intravenous doses. • A post-treatment Follow-Up Period of 84 (± 3) days following the last dose of AK002. 
If doses are considered skipped or missed, the total study duration will be extended beyond 28 months. The 84-day (± 3) post-treatment Follow-Up Period still applies after the last dose of study drug.

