Statistical Analysis	Summary statistics will include the mean, median, standard deviation, minimum, and maximum for continuous variables and number and percentage of patients for categorical variables). No imputation will be used for missing data. Data will be analyzed as laid out in the Statistical Analysis Plan.
Rationale for Amendment 7	
The following modifications were incorporated into Amendment 7:
 
 Clarified that doses more than 15 days out of window will be considered skipped in order to standardize out-of-window deviations and get patients back on dosing track. Clarified that any doses skipped or missed during the initial 701 days may be made up after Day 701 (26th dose) to give all patients a chance to receive a total of 26 doses. Updated total duration of time to reflect the possibility of skipped/missed doses being made up after Day 701 and therefore extending the treatment period duration. Changed Exclusion Criterion 4 to allow for COVID-19 vaccinations of any kind, including live, attenuated vaccines. Updated total number of patients treated with AK002. Clarified that male patients do not need to discontinue the study if their partner becomes pregnant, but the pregnancy must be followed to term. Corrected Schedule of Assessments for Day 547 being an EGD day, not an infusion day. Removed Baseline Diet compliance from histology Days 211 and 547. Updated Appendix 19.8 to reflect that biopsy samples may be used for further research in the future.

2. Background

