Patients will receive up to 26 monthly intravenous infusions of AK002 in an open-label manner. The first infusion of AK002 will be 1 mg/kg, and subsequent infusions will be 3 mg/kg.

If a monthly infusion of AK002 is missed the patient will be permitted to make up the missed dose after the 26th month so that all patients have the chance to receive a total of 26 infusions.

An EGD with biopsy will occur on Day 211 (± 3), Day 547 (± 3), and Day 729 (± 3) or 28 (± 3) days after the last dose of study drug, if early termination (ET) or if patient received additional missed doses.

Patients will be followed for 84 (± 3) days after the last dose of study drug. Follow-up visits will occur on Extension Day 736 (± 3), Day 757 (± 3), and Day 785 (± 3) or 35 (± 3), 56 (± 3), and 84 (± 3) days after last dose of study drug, if ET or if patient received additional missed doses.

Total duration of Study AK002-003X will be approximately 28 months if doses are administered monthly and none are missed, or longer, as needed for the patient to receive all 26 doses.

Approximately 60 patients will be enrolled in Study AK002-003X, based on enrollment of Study AK002-003.

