5.2 Schedule of Events

The overall schedule of procedures and assessments is shown in [Table 1](#).

Table 1 Study AK002-003X Schedule of Assessments

Assessment Description	Prior to Dose 1	Treatment Period (25 months or longer if any monthly doses have been missed/skipped) ²⁰							Follow-Up Period (12 weeks)				
		Dose # 1 Day 1	Dose # 2 Day 29 (±3)	Doses #3–8 Day 57–197 ²⁶ (±3)	Day 211 (±3)	Doses #9–20 Day 225–533 ²⁷ (±3)	Day 547 (±3)	Doses #21–26 Day 561–701 ²⁸ (±3)	Additional Infusion Day(s) only if previous infusions have been missed ²⁹	Day 729 ¹ (±3) or 28 days after last dose	Day 736 ¹ (±3) or 35 days after last dose	Day 757 ¹ (±3) or 56 days after last dose	Day 785 ¹ (±3) or 84 days after last dose
Informed consent	X												
Prior/Concomitant Medications ²		X	X	X	X	X	X	X	X	X	X	X	X
Body weight ³		X ⁴ (predose)	X (predose)	X (predose)		X (predose)		X (predose)	X (predose)		X	X	X
Vital Signs ⁵		X ⁴	X	X		X		X	X		X	X	X
SF-36 Health Survey		X ⁴	X	X		X		X	X		X	X	X
ePRO Activation and Training ⁶	X												
ePRO Questionnaire (may include Additional Questions) ⁷		<----- Complete electronically one time daily ----->											
PGIC Questionnaire ¹³			X	X									
Baseline Diet Changes		X ⁴	X	X		X		X	X		X	X	X
Urine Dipstick Pregnancy Test ⁸		X ⁴	X	X		X		X	X		X		
Eligibility Assessment	X												
Current Safety Evaluations, as needed ⁹	X												
Access IRT to enter PID and current body weight ¹⁰		X	X	X		X		X	X				
Premedication: Prednisone ¹¹	X												
Study Drug Administration ¹²		X	X	X		X		X	X				
Symptom directed Physical Exam ¹⁴		X ⁴	X	X		X		X	X		X	X	X
Blood for Hematology with differential ^{15, 16}		X ⁴	X	X		X		X	X		X	X	X
Blood for Chemistry ^{15, 17}		X ⁴	X	X		X		X	X		X	X	X
Urinalysis ^{15, 18}		X ⁴									X		
Blood for PK ^{15, 19}		X ⁴									X		

Table 1 Study AK002-003X Schedule of Assessments

Assessment Description	Prior to Dose 1	Treatment Period (25 months or longer if any monthly doses have been missed/skipped) ²⁰								Follow-Up Period (12 weeks)			
		Dose # 1 Day 1	Dose # 2 Day 29 (± 3)	Doses #3–8 Day 57–197 ²⁶ (± 3)	Day 211 (± 3)	Doses #9–20 Day 225–533 ²⁷ (± 3)	Day 547 (± 3)	Doses #21–26 Day 561–701 ²⁸ (± 3)	Additional Infusion Day(s) only if previous infusions have been missed ²⁹	Day 729 ¹ (± 3) or 28 days after last dose	Day 736 ¹ (± 3) or 35 days after last dose	Day 757 ¹ (± 3) or 56 days after last dose	Day 785 ¹ (± 3) or 84 days after last dose
Blood for ADA ^{15, 20}		X	X	X		X ²⁰					X		

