- 22) See [Appendix 19.8](#) for biopsy assessments. EGD should occur on Day 211 (± 3), Day 547 (± 3) and Day 729 (± 3) or 28 (± 3) days after the last dose of study drug if the patient discontinues the study early or if previous missed infusions were made up, and patient agrees to have an early-termination biopsy.
- 23) Non-serious adverse events will be captured from Day 1 (first dose of study drug) through Day 785 or 84 days after last dose of study drug, if ET or if previous missed infusions were made up.

Table 1 Notes cont.

- 24) Adverse events of special interest will be captured from Day 1 (first dose of study drug) through Day 785 or 84 days after last dose of study drug, if ET or if previous missed infusions were made up.
- 25) Serious adverse events of special interest will be captured from Day 1 (first dose of study drug) through Day 785 or 84 days after last dose of study drug, if ET or if previous missed infusions were made up.
- 26) Monthly doses # 3–8 will occur on Days 57, 85, 113, 141, 169, and 197 (± 3 days).
- 27) Monthly doses # 9–20 will occur on Days 225, 253, 281, 309, 337, 365, 393, 421, 449, 477, 505, and 533 (± 3 days).
- 28) Monthly doses # 21–26 will occur on Days 561, 589, 617, 645, 673, and 701 (± 3 days).
- 29) *Only if previous infusions have been missed*, make-up dosing may occur on Day 701 + 28 days (± 3), until 26 total doses have been administered.
- 30) Doses will be considered missed if they occur more than 15 days outside the protocol-specified window.

6. Criteria for Evaluation

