9.4 Study Drug Dosage/Dosage Regimen

The first infusion of AK002 will be 1 mg/kg. Starting with the second infusion (Extension Day 29), the dose of AK002 will be increased to 3 mg/kg, and 3 mg/kg will be administered for all subsequent infusions.

Dosing will occur on Extension Days 1, 29, 57, 85, 113, 141, 169, 197, 225, 253, 281, 309, 337, 365, 393, 421, 449, 477, 505, 533, 561, 589, 617, 645, 673, and 701 (± 3 days).

If a monthly infusion is delayed so that it occurs closer in the time frame to the next upcoming infusion, the late infusion will be considered skipped and may be made up after Day 701. Therefore, dosing could possibly occur on Day 729 (makeup for 1 skipped dose) and every 28 (± 3) days after that, until 26 doses in total have been received.

The exact dose will be calculated prior to each infusion and based on current patient body weight. Study drug will be administered as a single peripheral intravenous infusion using an infusion pump as indicated in the study Pharmacy Manual at the study visits specified in [Table 1](#).

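### Table 1 note 30 and the midpoint rule in Section 9.4 and the synopsis set uncoordinated cut-offs for a skipped or missed dose: on nominal days, 19 days late against 15

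*Combined protocol and SAP*

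**What the plan says.** Section 9.4 fixes the dosing calendar ("Dosing will occur on Extension Days 1, 29, 57, 85, 113, 141, 169, 197", and so on to Day 701), with ±3 days around each date. It then gives a midpoint rule: an infusion is skipped when it is "delayed so that it occurs closer in the time frame to the next upcoming infusion, the late infusion will be considered skipped". The synopsis, under Test Product, Dose, and Administration, repeats this rule and its consequence: "the late infusion will be considered skipped and may be made up after Day 701".

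Table 1 note 30, in Section 5.2, uses a fixed count: "Doses will be considered missed if they occur more than 15 days outside the protocol-specified window".

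Skipped and missed are treated as one status. The Table 1 header pairs them ("25 months or longer if any monthly doses have been missed/skipped"), and the Amendment 7 rationale in the synopsis gives them the same consequence ("any doses skipped or missed during the initial 701 days may be made up after Day 701"). Making up a dose is optional: under Section 5.1, "the patient will be permitted to make up the missed dose after the 26th month".

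**The concern.** Two rules classify the same event, neither refers to the other, and no section says which governs. The classification decides whether a late 3 mg/kg infusion is given or is dropped and possibly made up after Day 701. Two sites following different pages of the same protocol could treat the same late visit differently. The site relying on note 30 would place two infusions closer together than Section 9.4 allows.

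**Working it through.** **Inputs.** The 26 listed dosing days are all 28 days apart (Section 9.4). The window is ±3 days. Note 30 uses 15 days. Let *d* be days after the dose's own nominal day, and *N* the number of days from that nominal day to the next infusion: 28 if it is on its nominal day, 25 to 31 across its window.

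**Rules as inequalities.**
- Midpoint rule: skipped if *N* − *d* < *d*, so *d* > *N*/2. At *N* = 28, *d* > 14: skipped from day 15.
- Note 30, literal (counted from the window edge): missed if *d* − 3 > 15, so *d* > 18: from day 19.
- Note 30, if counted from the nominal day: *d* > 15: from day 16.

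**Days late on which the rules give different cut-offs.**

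| Next infusion (*N*) | Midpoint rule applies from | Differ, note 30 literal | Differ, note 30 from nominal day |
|---|---|---|---|
| 25 | 13 | 13–18 | 13–15 |
| 26 or 27 | 14 | 14–18 | 14–15 |
| 28 (nominal) or 29 | 15 | 15–18 | 15 |
| 30 or 31 | 16 | 16–18 | none |

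The table measures lateness from the dose's own nominal day. If the midpoint is taken between the end of the dose's own window and the start of the next window, the literal difference is again days 15–18. If it is taken between the end of the own window and the day of the next infusion, the difference is days 16–18 at *N* = 28 and day 18 alone at *N* = 31.

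**Worked example.** Dose 5 is due on Day 113 (window to Day 116), and dose 6 on Day 141 (window from Day 138).
- Day 127 (14 late): 141 − 127 = 14, which is not closer to dose 6. Neither rule applies.
- Day 128 (15 late): 141 − 128 = 13 < 15, so skipped under Section 9.4. For note 30, 128 − 116 = 12 and 128 − 113 = 15; neither exceeds 15, so it does not apply on either count.
- Day 131 (18 late): 141 − 131 = 10 < 18, so skipped under Section 9.4. Literally, 131 − 116 = 15, so note 30 does not apply. From the nominal day, 18 > 15, so it does.
- Day 132 (19 late): 132 − 116 = 16 > 15. Both rules apply.

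**Shortest gap to the next dose under each cut-off.**

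| Cut-off used | Last day not skipped or missed | Gap to Day 141 | Gap to Day 138 |
|---|---|---|---|
| Section 9.4, nominal days | 127 | 14 | 11 |
| Note 30 from nominal day | 128 | 13 | 10 |
| Note 30 literal | 131 | 10 | 7 |

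**The case against.** The strongest reply is that this is not a contradiction. Both rules say when a dose *is* skipped or missed; neither says when it is *not*, and note 30 does not authorise an infusion. A dose 16 days late that Section 9.4 skips stays skipped, because note 30 is silent on it. This stands: a site that applies both rules is in effect using the earlier cut-off and breaches nothing. But no text gives that instruction. On that reading note 30 also adds nothing for a late dose that has a scheduled successor, although the Amendment 7 rationale presents the 15-day count as a clarification.

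The second reply is that note 30 may have meant 15 days from the nominal day. Table 1 note 11 speaks of a 28-day treatment window, which lends this some support. The mismatch at nominal spacing then shrinks to day 15. Against it, note 30 counts from outside the window, and the rationale does the same: "Clarified that doses more than 15 days out of window will be considered skipped". The rationale is used here only as evidence of where the count starts.

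Third, a site deciding on a late dose would naturally measure to the scheduled day of the next one, so the results for other positions of the next infusion matter less than the nominal row. That is fair, and the conclusion rests on the nominal row.

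A reader might infer that a safety limit is breached or that results would be affected. The documents support neither. They state no minimum interval that a 10-day gap would cross. Note 11 already provides an eosinophil check, with prednisone and a slower infusion if eosinophils are no longer suppressed, for patients well outside the treatment window. Section 15 plans no formal inference, and Section 15.2 defines only a Safety population of treated patients.

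**Conclusion.** The cut-offs are uncoordinated and should be aligned. With note 30 read literally and the next dose at its nominal day, the rules differ for doses 15 to 18 days late. A site using note 30 as its cut-off could infuse 10 days before the next nominal dose (7 at its early window edge), against at least 14 (11) under Section 9.4. Counted from the nominal day, the difference is day 15 only.

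This assumes that lateness is measured from the dose's own nominal day and that some sites would work from note 30 alone. The documents do not say how often doses run this late. It is a minor dosing-consistency correction: no analysis set, method or inference depends on it. The tempting stronger claim, that the two rules cannot both be obeyed, fails because the earlier cut-off satisfies both.

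**What to change.** Put one rule, with a stated counting origin, in note 30, Section 9.4 and the synopsis:

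*A dose is considered skipped/missed if it would occur more than 14 days after its scheduled (nominal) day; it may be made up after Day 701.*

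This keeps the midpoint rule on nominal days, removes any dependence on where the next infusion falls in its window, and covers dose 26, which has no scheduled next dose. A cut-off of 15 days after the nominal day should not be offered as the sponsor's intention, because the sponsor's text counts from the window.

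The cost is one sentence in three places. Relative to Section 9.4 on nominal days, nothing is reclassified. Relative to literal note 30, doses 15 to 18 days late become optional make-ups, each adding 28 days for that patient if taken. One make-up puts the last dose on Day 701 + 28 = 729, the final EGD on Day 729 + 28 = 757, and follow-up on Days 764, 785 and 813 (729 + 35, + 56 and + 84).

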6.1 Safety Endpoints

The safety and tolerability of AK002 will be assessed by determining the following:

- Symptom-directed physical examination (Section 11.3.3)
- Changes in body weight (Section 11.3.2) and vital signs (Section 11.3.4)
- Hematology (Section 11.2.4)
- Changes in concomitant medication use due to AE (Section 11.3.1)
- Blood chemistry (Section 11.4.2)
- Urinalysis (Section 11.4.4)
- ADA (Section 11.4.5)
- Adverse events (Section 13.)

6.2 Pharmacokinetic Endpoints

Blood (serum) will be collected for assessment of AK002 concentrations using a validated enzyme-linked immunosorbent assay method. Blood (serum) will be collected for assessment of ADA to AK002 using a validated assay method.

Pharmacokinetic blood samples will be obtained predose on Extension Day 1 (obtained from Day 113 evaluations of Study AK002-003 or redrawn for patients that were discontinued from treatment in AK002-003) and on Extension Day 561 (± 3) and Extension Day 736 (± 3) or 35 (± 3) days after last dose of study drug, if ET or if patient received additional missed doses.

ADA samples will be obtained predose on Extension Day 1, predose on all infusion days through Extension Day 365, on Extension Day 533 (± 3), and on Extension Day 736 (± 3) or 35 (± 3) days after last dose of study drug, if ET or if patient received additional missed doses.

6.3 Efficacy Endpoints

Daily self-administration of a disease-specific patient questionnaire (PRO Questionnaire) will be used to evaluate signs and symptoms associated with EG and/or EoD. Changes in quality of life will be measured by the Short-Form 36 Health Survey (SF-36) questionnaire. Changes in the number of eosinophils in gastric and/or duodenal mucosa from baseline will also be evaluated.

6.4 Pharmacodynamic Endpoints

Change in blood eosinophils will be assessed at study visits.

7. Patient Selection

7.1 Number of Patients

Approximately 60 patients will be enrolled in Study AK002-003X.

7.2 Study Population

Patients who complete Study AK002-003 or were discontinued from treatment in Study AK002-003 study for high eosinophil counts prior to infusions 2, 3, or 4 and meet the inclusion criteria in Section 7.3 and exclusion criteria in Section 7.4 will have the option to receive AK002 in an open-label manner. A patient is categorized as having completed Study AK002-003 if 4 infusions of study drug were administered and the patient was followed through Day 113 (± 3) of Study AK002-003.

7.3 Inclusion Criteria

Patients are eligible for the study if all of the following criteria are met:

- 1) Provide written informed consent.
- 2) Completed Study AK002-003, defined as having received 4 infusions of study drug and followed through Day 113 (± 3) in Study AK002-003 or discontinued from treatment due to high eosinophil counts prior to infusions 2, 3, or 4, and willing to begin extended dosing on or about Day 113 (for AK002-003 completers) or within 6 months of last dosing for patients discontinued from treatment.
- 3) If patient is on pre-existing dietary restrictions, willingness to note any changes that occur from the Baseline diet, throughout the study.
- 4) Able and willing to comply with all study procedures.
- 5) Female patients must be either post-menopausal for at least 1 year or surgically sterile (tubal ligation, hysterectomy, or bilateral oophorectomy) for at least 3 months, or if of childbearing potential, have a negative pregnancy test and agree to use dual methods of contraception, or abstain from sexual activity until the end of the study, or for 120 days following the last dose of study drug, whichever is longer.
- 6) Male patients with female partners of childbearing potential must agree to use a highly effective method of contraception until the end of the study or for 120 days following the last dose of study drug, whichever is longer. All fertile men with female partners of childbearing potential should be instructed to contact the Investigator immediately if they suspect their partner might be pregnant at any time during study participation.

7.4 Exclusion Criteria

Patients will be excluded from the study if they meet any of the following criteria:

- 1) Poor tolerance to previous administration of AK002 in the opinion of the Investigator.
- 2) Known hypersensitivity to any constituent of the study drug.
- 3) Any disease, condition (medical or surgical), or cardiac abnormality, which, in the opinion of the Investigator, would place the patient at increased risk.
- 4) Vaccination with live attenuated vaccines within 30 days prior to initiation of treatment in the study, during the treatment period, or vaccination expected within 5 half-lives (4 months) of study drug administration. All types and formulations of vaccines (including live attenuated vaccines) authorized by FDA or other regulatory authority for the prevention of COVID-19 may be administered before, during, or after this study. The vaccine should not be administered within 7 days prior to and within 7 days after the administration of AK002 so that any side effects caused by either of the 2 medications can be more easily determined.
- 5) Women who are pregnant, breastfeeding, or planning to become pregnant while participating in the study.
- 6) Any other reason that, in the opinion of the Investigator or Medical Monitor, makes the patient unsuitable for enrollment.
- 7) Diagnosis of Hypereosinophilic Syndrome (HES) based on standard criteria (blood eosinophils $>1500/\mu\text{L}$ with involvement of either the heart, nervous system, and/or bone marrow).

8. Concurrent Medications

Concomitant medications include both prescribed and over-the-counter medications and will be recorded in the electronic Case Report Forms (eCRF).

Any medication must have been stopped as required in AK002-003 exclusion criteria. Patients should be advised against taking any new medication, both prescribed and over-the-counter, without consulting the Investigator, unless the new medication is required for emergency use. Immediately prior to the first infusion, the study site personnel should ensure that the patient continues to meet the inclusion criteria and none of the exclusion criteria (including no receipt or use of prohibited medications).

All medications taken during participation in this study must be documented on the eCRF. All medications used to treat IRR or AE must also be documented.

